2.4 ENDPOINTS

Primary Endpoints

Feasibility: An indication of feasibility assessed by calculating treatment adherence indicators such as the average number of therapy sessions completed by participants, the percentage of participants completing different components of the intervention (face-to-face sessions, phone calls), and attrition (the percentage who complete post-intervention assessment).

Acceptability: An indication of acceptability assessed by calculating scores on Credibility/Expectancy Scales, the Client Satisfaction Questionnaire, User Experience Questionnaire and other bespoke acceptability measures identified by the YPAG, and by analysing qualitative data obtained through the Experience of Service questionnaire and semi-structured feedback interviews.

Safety: Safety of the intervention determined by reviewing *adverse events* recorded at each assessment and therapy session/phone call contact.

Secondary Endpoints

Potential effectiveness of the IMAGINATOR intervention:

Change assessed from pre-FIT intervention to post-FIT intervention, and at 6 months follow up in the following outcomes:

- a) Average frequency of self-harm, and average severity of self-harm scores over the past 3 months
- b) Average scores on questionnaires of clinical, functional and process outcomes (see Assessments)
- c) Proportion of YP needing further treatment in CCAMHS/MINT/other WLT services vs can be closed to CCAMHS/MINT/other WLT services
- d) Emergency department visits.

Potential mechanisms:

Change assessed from pre-FIT intervention to post-FIT intervention, and at 6 months follow up in the following outcomes:

- a) Average scores on characteristics of mental imagery associated with self-harm when present (e.g. vividness, compellingness)
- b) Average scores of the urge to self-harm
- c) Average scores on emotion regulation ability measures.

Potential effectiveness of the *IMAGINATOR* app:

a) Correlations between endpoint scores (listed above) and the following measures of *IMAGINATOR* app use: number of app sessions/logins and total duration of app use, number of activity cycles completed, number of personalised media uploaded, number of completed guided imagery sessions, total duration of guided imagery completed and use of any other key functionalities at 6 months follow up.

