To assess risk and adverse events, at the beginning of each session the therapist conducts the Columbia-Suicide Severity Rating Scale (C-SSRS) interview.

Follow-up Phase

Follow up and support sessions: The Follow Up phase involves five support phone calls by the therapist/CWP/CAPT who conducted the FIT. The first phone support takes place one week after the second FIT session (approx. 30 mins duration). This session focuses on refining the functional imagery practice and problem-solving obstacles to training the imagery techniques. Suggestions - aim to incorporate the *IMAGINATOR* app as much as possible if the participant feels this is useful, for example discussing how the different app functionalities can be used, personalised and maximised to support the FIT.

Four further phone support sessions (approx. 15 mins each) are then delivered fortnightly, which focus on further problem-solving, motivational encouragement and discussion of how to maximise the *IMAGINATOR* app use.

To assess risk and adverse events, the therapist will conduct a clinical risk assessment at the beginning of each phone session.

IMAGINATOR app-based support: The IMAGINATOR app was co-designed with YP with lived experience of self-harm (see 2.2. Co-production). It is used by participants as a support to keep practicing and training FIT to achieve their behavioural change goal during the study follow-up IMAGINATOR 2.0

phase. The IMAGINATOR app does not introduce any new element from what has been discussed and developed in the FIT face-to-face sessions and is neither intended to nor designed to be used as a self-standing tool. To ensure confidentiality, the IMAGINATOR app makes no reference to self-harm and all push-ups and notifications only refer to 'IMAGINATOR'.

Routine follow-up: The therapist/CWP/CAPT) will follow up routinely with the young person at 16 – 18 weeks.

Outcome Assessments (post intervention and 6 months follow-up)

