measurement of suicidal ideation and behaviour. The *Lifetime/Recent* version will be used at screening to gather recent history of suicidality including suicidal ideation and/or behaviour. The scale measures four constructs: severity of ideation on a 5-point ordinal scale (from 1=wish to be dead, to 5=suicidal intent with plan); intensity of ideation via 5 items (e.g. frequency, duration etc.), each rated on a 5-point ordinal scale; behavior rated on a nominal scale (including actual, aborted, and interrupted attempts, preparatory behavior and non-suicidal self-injurious behavior); and lethality rated on a 6-point ordinal scale. **This measure will additionally be used at the start of each face-to-face FIT session.**

e) Motivation to reduce self-harm: Using the State Motivation for Reducing Self-harm (SM-SH) scale (Parham et al., 2017). This scale measures participants' motivation to control their self-harm using 12 items that measure the strength of their motivational cognitions in the present moment, rated on a 10-point likert scale, from 0 (never) to 10 (constantly).

Self-report:

f) Urge to self-harm: Using the Craving Experience Questionnaire for Self-Harm (CEQ-SH), adapted from CEQ (May et al., 2014) This questionnaire assesses the urge to self-harm and assesses frequency, intensity, salience or dismissability of intrusive thoughts surrounding self-harm. It is rated on a 10 point Likert type scale ranging from not at all (0) to constantly (10).

Clinical and functional measures

Self-report:

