3.2 RISKS AND BENEFITS

Risks: There are only low foreseeable serious risks associated with this project. The treatment protocol of FIT is in keeping with NICE guidelines and current psychological interventions for self-harming behaviour. Elements included in FIT such as motivational interviewing, formulation of drivers of self-harm and use of mental imagery techniques for targeting self-harm are part of established psychological therapies such as cognitive-behavioural therapy, dialectical-behavioural therapy and schema therapy commonly used for individuals who self-harm. Our previous study using this protocol reported no adverse events ([name] et al., 2020).

Participants' wellbeing and safety will be taken into account as a priority concern at all points in the study.

However, theoretically it is possible that a number of procedures (listed below) included in the study may result in *causing increased levels of distress*. If this would be the case the necessary steps to guarantee the participant's wellbeing and safety will be taken as described below.

Study procedures that ask to recall information about current and past psychological problems and/or current and past problematic experiences may result in (*i*) *i.e. increased perceived distress* and/or (*ii*) *i.e. disclosure of information relevant for the participants' mental health and safety.* These include:

- responding to questionnaires during the Baseline Screening Visit and the Outcome Assessments (see 3.6 and 3.7);
- answering questions that investigate details of self-harm behaviour and associated emotions during the FIT sessions and during the follow up phone support sessions (see 3.6).

The *risk (i), i.e. of major distress* being caused by the above study procedures will be minimised in three major ways:

Firstly, participants will be fully informed about the content of the outcome assessments (such as questionnaires including questions about mood, self-harm behaviour, alcohol and drug use) so that they can prepare themselves and give fully informed consent to participate. Equally, they will be fully informed and prepared with regards to the contents and procedures of the FIT intervention. Research has demonstrated that asking about self-harming behaviors does not increase risk of harmful outcomes (Polihronis et al., 2020) but instead may in fact give participants an opportunity to contribute to research and to "tell their story" (Biddle et al., 2013).

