3.3 ADVERSE EVENTS

Definitions

Adverse Event (AE): any untoward medical occurrence in a patient or clinical study subject.

Serious Adverse Event (SAE): any untoward medical occurrence or effect that:

- Results in death
- Is life-threatening refers to an event in which the subject was at risk of death at the time of the event; it does not refer to an event which hypothetically might have caused death if it were more severe
- Requires hospitalisation, or prolongation of existing inpatients' hospitalisation
- Results in persistent or significant disability or incapacity
- Is a congenital anomaly or birth defect

Medical judgement will be exercised in deciding whether an AE is serious in other situations. Important AEs that are not immediately life-threatening or do not result in death or hospitalisation but may jeopardise the subject or may require intervention to prevent one of the other outcomes listed in the definition above, will also be considered serious.

Reporting Procedures

All adverse events will be reported. Depending on the nature of the event the reporting procedures below will be followed. Any questions concerning adverse event reporting will be directed to the Chief Investigator in the first instance.

Non serious Aes: All such events, whether expected or not, will be recorded- it will be specified if only some non-serious Aes will be recorded, any reporting will be consistent with the purpose of the trial end points.

Serious Aes: An SAE form will be completed and emailed to the Chief Investigator within 24 hours. However, hospitalisations for elective treatment of a pre-existing condition will not need to be reported as SAEs.

All SAEs will be reported to the West of Scotland REC 5 where in the opinion of the Chief Investigator, the event was:

- 'related', ie resulted from the administration of any of the research procedures; and
- 'unexpected', ie an event that is not listed in the protocol as an expected occurrence

Reports of related and unexpected SAEs will be submitted within 15 days of the Chief Investigator becoming aware of the event, using the NRES SAE form for non-IMP studies. The Chief Investigator will also notify the Sponsor of all related and unexpected SAEs.

Local investigators will report any SAEs as required by their Local Research Ethics Committee, Sponsor and/or Research & Development Office.

Contact details for reporting SAEs	
[contact]	
CI email (and contact details below)	
Email: [contact]	

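### The methods named for finding adverse events are narrower than the primary safety endpoint, and no distress check is linked to the adverse-event record

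*Combined protocol and SAP*

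**What the plan says.** Section 2.4 makes safety one of three primary endpoints: "Safety of the intervention determined by reviewing" adverse events that are "recorded at each assessment and therapy session/phone call contact". Section 2.8 repeats the recording rule. Section 3.3 defines an adverse event as "any untoward medical occurrence in a patient or clinical study subject".

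Section 2.7 states how events are to be looked for. For the FIT sessions: "To assess risk and adverse events, at the beginning of each session the therapist conducts the Columbia-Suicide Severity Rating Scale (C-SSRS) interview". For the support calls it gives the same purpose, but the method is that "the therapist will conduct a clinical risk assessment at the beginning of each phone session". No instrument, item list or recall period is given for the calls. Section 2.8 confines the extra C-SSRS use to the sessions: "This measure will additionally be used at the start of each face-to-face FIT session".

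Section 3.2 foresees study procedures "causing increased levels of distress", and lists questions put during FIT sessions and calls, as well as the questionnaires, as possible sources.

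Section 3.3 provides a form for serious events only. For non-serious events it says that all will be recorded, then adds what looks like an unfinished template clause about recording only some of them.

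**The concern.** A safety endpoint can be no broader than the questions that feed it. Here the definition takes in any untoward occurrence, while the one tool named and described asks about suicidal thoughts, suicidal behaviour and self-injury. For most therapy contacts the content of the enquiry is not stated at all. An event outside the C-SSRS reaches the record at a session only if the therapist happens to ask or the participant mentions it. At a call, it depends on whatever the risk assessment contains.

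This matters most for distress brought on by the sessions, the imagery work or the app. It is the harm the protocol expects, and the study takes a revised intervention and a new app to a younger group (section 2.1). Sections 1 and 3.2 already cite the absence of adverse events in the earlier proof-of-concept study. A similar result here would be hard to interpret without knowing what participants were asked.

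**Working it through.** **1. The plan's own figure.** Section 2.9 wants 15 completers with 25% attrition: 15 / (1 − 0.25) = 20, which matches the stated enrolment. It is not in dispute and is used below only to count contacts.

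**2. Contacts by method** (3 sessions and 5 calls per participant, sections 2.5 and 2.6).
- Per participant: 3 + 5 = 8 contacts; calls are 5/8 = 62.5%.
- At N = 20: 60 sessions and 100 calls, 160 in all.
- At N = 15: 45 sessions and 75 calls, 120 in all.

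**3. What is asked, and where it goes.**

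| Contact | Method named for adverse events | Other check that touches distress | Stated link to the adverse-event record |
|---|---|---|---|
| FIT sessions (3) | C-SSRS: ideation, behaviour including self-injury, lethality (2.8) | RCADS subscale(s) or DASS-21 (2.7); staff alert to signs of distress (3.2) | None |
| Calls (5) | Clinical risk assessment, content not stated (2.7) | Staff alertness (3.2); unclear whether the symptom scales extend to calls | None |
| Outcome assessments (2) | Recording required (2.4, 2.8); no adverse-event question given | Researcher checks mood and safety (3.2); symptom scales (2.8) | None |

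No row contains a general adverse-event question, a question on whether the intervention left the participant worse, or a threshold at which distress counts as an event.

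**4. What is picked up later.** Section 2.5 puts the calls in weeks 4, 6, 8, 10 and 12. Section 2.7 puts the first call one week after the second session; with weekly sessions starting in week 1, that gives weeks 3, 5, 7, 9 and 11. The two sections must be reconciled, but either way the calls span 8 weeks. The post-intervention assessment falls about a week after the last call, so its three-month look-back at self-harm (section 2.8) covers 8 + 1 = 9 weeks with room to spare. The C-SSRS is repeated there, and emergency attendances come from clinical records. Self-harm and suicidal events from the call period are therefore largely recovered among those who attend. On the plan's attrition figure, 20 × 0.25 = 5 participants may not complete follow-up. Other kinds of event have no such second chance.

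**5. Size.** The documents give no detection rates, so under-counting cannot be estimated. As an illustration only, suppose no participant has a recorded event. The one-sided 95% upper bound is 1 − 0.05^(1/n). If only a share *s* of affected participants is detected (an assumption), the bound on the true proportion is that value divided by *s*.

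| n | s = 1 | s = 0.7 | s = 0.5 |
|---|---|---|---|
| 20 | 13.9% | 19.9% | 27.8% |
| 15 | 18.1% | 25.9% | 36.2% |

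**The case against.** The strongest reply is that adverse-event recording is not limited to the two named methods. Sections 2.4 and 2.8 require it at every contact, section 3.3 says that all non-serious events are recorded, and the calls are made by the same clinician who gave the sessions. This is fair as a duty to record. It does not say what is asked, and the clause on non-serious events is unresolved. Also, one page after the adverse-event reporting text was not available for this review, so a tool described there cannot be excluded. The sections cited here do not refer to one.

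Four stronger readings are tempting, and the documents do not support them.

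- *Distress is never asked about.* Section 2.7 has RCADS or DASS-21 at each therapy session and a check before the baseline visit ends. Section 3.2 has mood checks at the baseline and outcome visits. A post-treatment feedback questionnaire and interviews cover experience of the intervention. The gap is that none of these is tied to the safety endpoint.
- *The calls use an unstructured, weaker method.* The plan does not describe the call assessment. It may follow the Trust's routine procedures and could be broader than the C-SSRS. Unspecified is all that can be said.
- *Event rates by phase are spoiled.* No such comparison is planned: safety is a review of events and the analysis is descriptive. Any figure for an apparent fall simply returns the assumed detection rates: 0.9 at sessions and 0.5 at calls gives a ratio of 0.5/0.9 = 0.56, while 0.9 at both gives 1.00.
- *The method changes just as app support takes over.* The app is installed at the end of the second session, so its use starts while C-SSRS sessions continue.

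**Conclusion.** The point holds in a limited form. Followed as written, the enquiry behind a primary endpoint is narrower than that endpoint at the three FIT sessions and undescribed at the five calls, and no distress check feeds the adverse-event record. The likely effect is under-counting of events other than suicidality and self-harm, above all distress attributable to the intervention. The size cannot be derived from the documents; the bounds in the working show only how far a zero count could mislead under assumed detection.

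The conclusion rests on the C-SSRS covering what section 2.8 says it covers, and on no adverse-event form or prompt existing in material not seen. It invalidates no planned analysis and changes no sample size. It is a cheap improvement worth making, because review of adverse events is the study's only safety endpoint.

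**What to change.** - Ask one fixed adverse-event question, with the same wording and recall period, at all 8 therapy contacts and both outcome assessments. Include whether the sessions, the imagery or the app left the participant feeling worse.
- Record answers on a single adverse-event form, with a written rule for when distress is entered as an event. State whether a worsening RCADS or DASS-21 score, or a failed mood check, triggers an entry.
- Settle the open clause in section 3.3 on which non-serious events are recorded.
- Report events by how they were found: solicited or spontaneous.
- Reconcile the timing of the first call between sections 2.5 and 2.7, so that the recall periods join up.

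The cost is one form and about a minute per contact: 10 askings × 20 participants = 200 minutes at most. The downside is that more non-serious events will be recorded, so the count should not be set beside the earlier study's without saying how each was obtained. The clinical risk assessment stays as the sponsor has set it.

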2.8 ASSESSMENTS AND QUESTIONNAIRES

1) The following measures are collected during the **Baseline Screening Visit** and again during the **Outcome Assessments (post intervention and at 6 months follow-up):**

Self-harm measures

Administered by researcher:

- a) Self-harm frequency over the past 3 months: Using the timeline follow-back technique (TLFB, Sobell & Sobell, 2008). This is an interview method conducted by the researcher who reconstructs together with the participant the number of self-harm behaviours using calendar cues. It has been successfully used in previous self-harm research including our proof-of-concept study ([name] et al., 2020; Maschauer et al., in preparation).
- b) Self-harm severity over the past 3 months: A combined measure of a Visual Analogue Scale, severity criteria used in the NSSI disorder in the Diagnostic and Statistical Manual of Mental Disorder Fifth Edition (DSM-V, 39) and the number of different self-harm methods used (also termed self-harm versatility), elicited via these open questions: "In the last three months, how severe was the worst injury that you inflicted to yourself? Can you list all the ways that you have used to harm yourself in the last three months?" This method was advised by the YPAG to avoid scales listing numerous self-harm methods which could be triggering/enabling.
- c) **Mental imagery related to self-harm:** Using the *Self-Harm Imagery Interview* adapted from (Hales et al., 2011): This interview is about mental images that deal with self-harm or occur with self-harm. It asks participants to think about one of these and explores their thoughts and emotions in relation to the image.
- d) Suicidal thoughts and behaviour: Using the *Columbia-Suicide Severity Rating Scale* (C-SSRS) (Posner et al., 2011) is widely used interview for suicide risk assessment and

measurement of suicidal ideation and behaviour. The *Lifetime/Recent* version will be used at screening to gather recent history of suicidality including suicidal ideation and/or behaviour. The scale measures four constructs: severity of ideation on a 5-point ordinal scale (from 1=wish to be dead, to 5=suicidal intent with plan); intensity of ideation via 5 items (e.g. frequency, duration etc.), each rated on a 5-point ordinal scale; behavior rated on a nominal scale (including actual, aborted, and interrupted attempts, preparatory behavior and non-suicidal self-injurious behavior); and lethality rated on a 6-point ordinal scale. **This measure will additionally be used at the start of each face-to-face FIT session.**

e) Motivation to reduce self-harm: Using the State Motivation for Reducing Self-harm (SM-SH) scale (Parham et al., 2017). This scale measures participants' motivation to control their self-harm using 12 items that measure the strength of their motivational cognitions in the present moment, rated on a 10-point likert scale, from 0 (never) to 10 (constantly).

Self-report:

f) Urge to self-harm: Using the Craving Experience Questionnaire for Self-Harm (CEQ-SH), adapted from CEQ (May et al., 2014) This questionnaire assesses the urge to self-harm and assesses frequency, intensity, salience or dismissability of intrusive thoughts surrounding self-harm. It is rated on a 10 point Likert type scale ranging from not at all (0) to constantly (10).

Clinical and functional measures

Self-report:

- a) Symptoms of low mood and anxiety: using 1) the Revised Children's Anxiety and Depression Scale (RCADS) for 12 17 year olds, is a 47 item youth self report questionnaire with six subscales (separation anxiety disorder, social phobia, generalised anxiety disorder, panic disorder, obsessive compulsive disorder, and low mood (major depressive disorder)) and a total anxiety scale and total internalising scale. The RCADS has good internal consistency, test-retrest reliability and convergent validity. 2) the Depression, Anxiety and Stress Scale (DASS-21) (Antony et al., 1998), for 18 25 year olds, a 21-item scale measuring levels of depression, anxiety and stress over the past week. It has acceptable to excellent internal consistency validated in both clinical and non-clinical samples. The depression scale measures symptoms associated with dysphoric mood e.g. worthlessness; the anxiety scale measures symptoms associated with physiological arousal such as trembling, as opposed to symptoms of generalised anxiety; and the stress scale measures symptoms of tension and reactivity to stressful events;
- b) **Psychological wellbeing:** using the Warwick-Edinburgh Mental Well-being Scale (WEMWBS) (Tennant et al., 2007), which consists of 14 positively worded items. Items are rated on a 5 point likert scale ranging between none of the time (1) and all of the time (5) with five

response categories and assesses mental wellbeing covering both hedonic and eudemonic perspectives.

- c) **Emotion regulation abilities:** using the *Difficulties in Emotion Regulation Scale-Short Form* (Kaufman et al., 2016), an 18-item scale adapted from the original long version that measures general emotion regulation ability as well as various aspects of emotion regulation (in six subscales), e.g. difficulties engaging in goal directed behaviour when upset, and limited access to emotion regulation strategies. The scale has high internal consistency.
- d) **Engagement in other risky, self-destructive behaviours** (e.g., binge eating, substance misuse): using the *11-item behaviour supplement to the Borderline Symptom List* (Bohus et al., 2001). The scale has high internal validity and test-retest reliability.
- e) Alcohol misuse/dependence: Alcohol Use Disorders Identification Test (AUDIT) (Saunders et al., 1993) This is a 10-item measure of alcohol misuse and possible dependence, in which participants are asked to rate items related to their drinking (e.g. 'How often do you have a drink containing alcohol') on a 5-point scale. The AUDIT is an effective means of identifying hazardous or harmful drinking behaviour.
- f) Cannabis misuse/dependence: Cannabis Use Disorder Identification Test Revised (CUDIT-R) (Adamson et al., 2010) This measure is used to screen for problem cannabis use. Participants are asked to rate a series of eight items relating to their cannabis use (e.g. 'How often do you use cannabis') on a 5-point likert scale. The measure has excellent internal consistency.
- g) Anhedonia: Anhedonia Scale for Adolescents (ASA) (Watson et al., 2021) is designed for use in 11-18 year olds and measures anhedonia on a 4 point likert scale using 15 questions. The ASA has high test-retest reliability. Temporal Experience of Pleasure Scale (TEPS) (Gard et al., 2006) captures a trait disposition to anticipation and consummation of pleasure using 18 items and a 6 point likert scale. The TEPS is internally consistent and temporally stable.

3) The following measures are collected once the intervention has started:

Acceptability measures

- a) **Credibility/Expectancy Questionnaire** (Devilly & Borkovec, 2000), is a short questionnaire measuring cognitively based credibility and affectively based expectancy of the therapy. The questionnaire has high internal consistency and good test-retest reliability. This will be used after the first face-to-face session.
- b) Client Satisfaction Questionnaire 8 item version (Attkisson & Zwick, 1982), provides a sensitive and comprehensive measure of patient satisfaction with the therapy received. This will be used post-treatment.

- c) User Experience Questionnaire (Laugwitz et al., 2008), assessed post-treatment (see Section 2.6 for details)
- d) Imaginator Feedback Questionnaire, administered post-treatment to obtain written feedback on the Imaginator intervention.
- e) **Adverse events** will be recorded at each assessment and therapy session/phone call contact.

Usability of the app

Engagement metrics will be collected directly from the app, including:

- a) Time to first access the app
- b) Total number of times accessed
- c) Total number of days/weeks the app accessed on
- d) Number of times used per week
- e) Duration of use per functionality.

Factors associated with app engagement:

- a) Questions relating to socioeconomic status, such as approximate yearly personal or parental income.
- b) Questions relating to technology/digital skills.

Feasibility and adherence to therapy protocol

An indication of feasibility will be assessed by calculating treatment adherence indicators, such as:

- a) Average number of therapy sessions completed by participants
- b) Percentage of participants completing different components of the intervention (face-toface sessions, phone calls)
- c) Attrition (the percentage who complete post-intervention assessment).
- d) Adherence to therapy protocol by therapists will be checked on a random sample of therapy session recordings against the therapy session checklist (part of the Imaginator manual).

Qualitative assessments

a) Semi-structured interview schedule developed using an established co-production methodology (Dewa et al., 2021a, 2021b), and used by the research team and YPAG during follow up interviews.

